5.1.1.1.2 Statistical Methods

The statistical methodology will be based on the use of the lower bound of the 2-sided 95% CIs of the ratio of post-vaccination GMTs between the QIV-HD and QIV-SD groups. The CIs will be calculated by normal approximation of log-transformed titers for GMTs.

The superiority objective will be achieved if it is demonstrated for the 4 strains in each age groups. Analyses will be performed for both the Full Analysis Set (FAS) and the Per-protocol Analysis Set (PPAS), but the conclusion will be made from PPAS results.

A sensitivity analysis will be performed with adjustment on the pre-vaccination HAI titers. Superiority objective will be analyzed on the PPAS and FAS through an analysis of covariance (ANCOVA) model, using the HAI titers at D0 as a covariate for adjustment, in order to account for the variability linked to the baseline HAI titer and to provide a "change from baseline" analysis.

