
Statistical Methods:
	
The per-protocol analysis set (PPAS) and full analysis set (FAS) will be used for the main immunogenicity analyses. Conclusions will be made based on the FAS results. The safety analysis set (SafAS) will be used for all safety analyses.
 
The statistical analysis will be performed in at least 2 steps:
 
 
• First analysis on immunogenicity and safety results obtained on data collected within the 28 days following the vaccination (from D0 to D28). The study blind will be broken at that time.
 
• Second analysis after the 6-month data have been collected.
 
 
Primary Objective
 
A superiority approach will be used to compare post-vaccination geometric mean titers (GMTs) between QIV-HD and QIV-SD groups for each strain and in each age group using a 1-sided test with Type I error rate of 0.025 following the individual hypotheses:

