### 12.2.3 Per-Protocol Analysis Set

The PPAS is a subset of the FAS. The subjects presenting with at least one of the following relevant protocol deviations will be excluded from the PPAS:

- Subject did not meet all protocol-specified inclusion criteria or met at least one of the protocol-specified exclusion criteria
- Subject did not receive vaccine
- Subject received a vaccine other than the one that he / she was randomized to receive
- Preparation and / or administration of vaccine was not done as per-protocol
- Subject did not receive vaccine in the proper time window
- Subject did not provide the post-dose serology sample at Visit 2 in the proper time window (ie, 28 to 35 days after vaccination) or a post-dose serology sample was not drawn at Visit 2
- Subject received medications impacting or that may have an impact on the immune response (Category 2 or 3)

The above protocol deviations leading to exclusion from the PPAS may be detailed and completed if necessary in the SAP, following the review of protocol deviations during the study conduct. In any case, the PPAS definition will be finalized before the first database lock.

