5.2.1 Full Analysis Set

The FAS is defined as the subset of randomized subjects who received the study vaccine and had a post-vaccination blood sample. Subjects will be analyzed according to the vaccine group to which they were randomized.

For the assessment of the immune response by virus SN and ELLA method, the analysis will be performed on the subjects from the FAS randomized into the respective observational subsets (FAS-SN subset and FAS-NA subset). The FAS-NA subset is a subset of the FAS-SN subset.

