5.2.2 Per-Protocol Analysis Set

The PPAS is a subset of the FAS. The subjects presenting with at least one of the following relevant protocol deviations will be excluded from the PPAS:

- Subject did not meet all protocol-specified inclusion criteria or met at least one of the protocol-specified exclusion criteria
- Subject did not receive vaccine
- Subject received a vaccine other than the one that he / she was randomized to receive
- Preparation and / or administration of vaccine was not done as per-protocol
- Subject did not provide the post-dose serology sample at V02 in the proper time window (ie, 28 to 35 days after vaccination) or a post-dose serology sample was not drawn at V02
- Subject received medications impacting or that may have an impact on the immune response (Category 2 or 3)

- Any other deviation identified during the study conduct and identified as relevant by the clinical team during data review, ie, indicated as excluding subjects from this analysis set in the manual deviations dataset.

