5.3.2 Immunogenicity

LLOQ and ULOQ management will be performed as described in [Section 4.4.1.3.5](#). No test or search for outliers will be performed.

No replacement will be done for missing values. Based on the previous QIV-HD and QIV-SD trials in this population, the amount of missing immunogenicity data is expected to be $\leq 5\%$ in this trial. Usually in vaccine trials, it seems generally reasonable to assume missing immunogenicity data are missing completely at random (MCAR) (2). Indeed, it is highly unexpected that the dropout (or any other reason for missing data) could be linked to the immune

response of the subject. Therefore, confirming the results of the PPAS for the primary analysis with the FAS would be satisfactory in terms of sensitivity analysis.

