5.5 Determination of Sample Size and Power Calculation

A total of approximately 1540 adults 60 years of age and older (770 adults 60 to 64 years of age and 770 adults 65 years of age and older) will be enrolled. This sample size is determined per simulations based on an overall power of 90% for demonstrating the primary objective. The thresholds for superiority are defined as 1 for GMTs. No alpha adjustment is needed. Other assumptions are listed as follows:

- Allocation ratio: 1:1 (QIV-HD versus QIV-SD)
- GMT ratio: 1.5 for all strains
- Standard deviations of log₁₀-transformed titers in QIV-SD group of 0.6 for 2 strains and 0.5 for the other 2 strains
- Attrition rate: 5% in FAS

It should be noted that the power per strain is 97.7% when the standard deviation is 0.6 and 99.7% when the standard deviation is 0.5.

An arbitrary number of subjects, ie, at least 50% of subjects in each age group and each vaccine group will be randomly assigned to the observational subset of subjects for SN testing and at least 50 subjects in each age group and each vaccine group for NA testing as shown in [Table 5.2](#).

Table 5.2: Random assignment of subjects to observational subsets

Vaccine/Assay	Number of subjects 60 to 64 years of age	Number of subjects 65 years of age and older	Total
QIV-HD Group/SN	≥ 193	≥ 193	≥ 386
QIV-SD Group/SN	≥ 193	≥ 193	≥ 386
QIV-HD Group/NA	≥ 50	≥ 50	≥ 100
QIV-SD Group/NA	≥ 50	≥ 50	≥ 100

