5.7 Changes in the Conduct of the Trial or Planned Analyses

Due to expected delay in availability of exploratory assays results, the first analysis may only address the HAI data for primary and secondary objectives, as well as safety data up to D28. Depending on their availability, SN and ELLA results may be analyzed in a second and/or final analysis. Therefore, the blind may be broken before the SN and ELLA results are released. As these are exploratory objectives, this does not raise any risk on the integrity on the main study conclusions.

In addition, unblinded information will not be communicated to the laboratories involved in these assays so we do not anticipate any risk of bias in these results.

6 References List

- 1 Newcombe RG. Two-sided confidence intervals for the single proportion: comparison of seven methods. *Stat Med.* 1998;17(8):857-72.

Document Number CLI_00252686	Version Number 2.0
Project Code Flu QIV HD	
Artifact Name Statistical Analysis Plan	

	Approver Name	Date (Universal Time)	Reason for Signature
Approval			I am approving this document
Approval			I am approving this document
Approval			I am approving this document
Approval			I am approving this document

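### The protocol synopsis decides the primary superiority claim on the FAS and the SAP decides it on the PPAS; SAP 5.7 does not record the switch, and the 90% power is shown only for the FAS

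*SAP*

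**What the plan says.** - **Protocol, Synopsis, Statistical Methods.** Both sets are used for the main immunogenicity analyses, and then: "Conclusions will be made based on the FAS results".
- **SAP 5.1.1.1.2.** Both sets are analysed, "but the conclusion will be made from PPAS results".
- **SAP 5.3.2.** The same assignment of roles appears again: "confirming the results of the PPAS for the primary analysis with the FAS would be satisfactory in terms of sensitivity analysis". The PPAS clause in 5.1.1.1.2 is therefore not an isolated slip.
- **Protocol 12.2.4 and SAP 5.2.5.** Both sets are analysed, and neither is named as decisive.
- **SAP 5.7.** The only change recorded is the late arrival of the SN and ELLA results and its effect on unblinding: "the first analysis may only address the HAI data for primary and secondary objectives". Nothing is said about the deciding set.
- **Protocol 12.5 and SAP 5.5.** The sample size allows for losses as follows: "Attrition rate: 5% in FAS". No rate is given for the PPAS.

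The opening of protocol section 12, including 12.1.1.1.1, was not in the text available to me, so I quote the FAS rule from the synopsis. The SAP front matter was also unavailable. The statement that the change is unrecorded therefore refers to SAP 5.7.

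**The concern.** A confirmatory trial needs one pre-specified set on which its claim stands or falls. Here a reader holding both documents could defend either.

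The sets differ in substance. The FAS needs only vaccination and a post-vaccination sample, and "Subjects will be analyzed according to the vaccine group to which they were randomized" (SAP 5.2.1). The PPAS also drops subjects for out-of-window samples, Category 2 or 3 medication, receipt of the wrong vaccine, and "Any other deviation identified during the study conduct and identified as relevant by the clinical team during data review" (SAP 5.2.2). Several of these arise after randomisation, and these subjects have measured titres. The missing-completely-at-random argument in SAP 5.3.2 concerns titres that are absent. It does not justify removing titres that exist.

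The overall objective needs superiority for all four strains in both age groups, which is eight tests. One result that changes between sets reverses the overall verdict. The planned power is also not shown for the set that the SAP uses.

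**Working it through.** **Inputs (SAP 5.1.1.1 and 5.5; protocol 12.5).** One-sided alpha 0.025; superiority threshold 1; GMT ratio 1.5, so δ = log10(1.5) = 0.1761; SD of log10 titre 0.6 for two strains and 0.5 for two; 385 per arm per age group; 5% loss in the FAS; success requires all eight tests. The SDs are stated for QIV-SD only, and I take them as equal in QIV-HD.

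**Formula.** For n evaluable per arm, the power per strain is P(T > t₀.₉₇₅), where T is noncentral t with 2n − 2 degrees of freedom and noncentrality δ / (SD·√(2/n)). With independent strains:

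- power per age group = (p₀.₆ × p₀.₅)²
- overall power = (p₀.₆ × p₀.₅)⁴

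**Reproducing the plan.** n = 385 × 0.95 = 365.75 gives 97.74% and 99.74% per strain, against 97.7% and 99.7% stated. Overall: (0.9774 × 0.9974)⁴ = 90.3%, against 90% stated. The plan's figure is correct for 5% loss, which it assigns to the FAS.

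**Power on the PPAS.** The PPAS is a subset of the FAS, so its total loss cannot be smaller. The documents give no rate. The losses below are assumptions.

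| Total loss to PPAS | n per arm | SD 0.6 | SD 0.5 | One age group | Overall, independent | Overall, correlation 0.5 |
|---|---|---|---|---|---|---|
| 5% (the FAS figure) | 365.75 | 97.74% | 99.74% | 95.1% | 90.3% | 91.5% |
| 10% | 346.5 | 97.11% | 99.62% | 93.6% | 87.6% | 89.2% |
| 15% | 327.25 | 96.32% | 99.44% | 91.7% | 84.2% | 86.4% |
| 20% | 308 | 95.32% | 99.19% | 89.4% | 79.9% | 83.0% |

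The last column is simulated with equally correlated strain statistics and independent age groups.

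Overall power falls below 90% at a total loss of about 5.7% with independent strains. That is n ≈ 363 per arm, about 3 fewer per arm per age group than the FAS allowance. With between-strain correlation 0.3, 0.5 and 0.7, the crossing is at about 7%, 8% and 11%.

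**How often the two sets would disagree.** Simulation assumptions: FAS loss 5%, PPAS nested in the FAS, random exclusions, true GMT ratio 1.5, and correlation √(n_PPAS / n_FAS) between the two statistics for the same strain.

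| Total loss to PPAS | Opposite overall verdicts, independent | Of which FAS succeeds, PPAS fails | Opposite overall verdicts, correlation 0.5 |
|---|---|---|---|
| 10% | 5.1% | 3.9% | 4.3% |
| 15% | 8.7% | 7.4% | 7.3% |
| 20% | 13.0% | 11.7% | 10.7% |

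At smaller losses disagreement is rarer: with independent strains, about 3.6% at 8% total loss and 1.9% at 6%. For a single age group it is about half the overall rate: 2.7%, 4.7% and 7.0% at 10%, 15% and 20%.

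**The case against.** The strongest reply accepts the contradiction and disputes its weight.

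- **The SAP agrees with itself on the deciding set.** Sections 5.1.1.1.2 and 5.3.2 both say PPAS. Stating attrition for the FAS is an omission for the PPAS rather than a second contradiction. That is fair. The conflict over the rule is between protocol and SAP, and the power point is secondary to it.
- **The sizes rest on assumed losses.** The only loss figure in the documents is 5%, and SAP 5.3.2 expects missing immunogenicity data of no more than that. This is true, and the shortfall cannot be fixed from the documents. But the 5% is already used up by the FAS, and PPAS exclusions come on top.
- **There is also a conclusion per age group.** SAP 5.1.1.1.1 allows superiority to be concluded within one age group, where the power loss and disagreement are smaller. This is correct, but SAP 5.1.1.1.2 still requires both age groups for the objective.
- **No bias or type I error inflation is shown.** With random exclusions the PPAS mainly loses power, which works against the sponsor's claim. The FAS also conditions on having a post-vaccination sample. Selection by arm is limited by blind data review (protocol 11.3), by code-breaking only after the first lock (protocol 6.4), and by the rule in protocol 12.2.3: "In any case, the PPAS definition will be finalized before the first database lock". All of this stands. It protects how the PPAS is formed, but it does not say which set decides. Protocol 12.2.3 lets the SAP detail the PPAS exclusions, not change the deciding set.
- **Both sets will be reported, so a disagreement would be visible.** It would be visible, but with no agreed rule for settling it.

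**Conclusion.** The concern holds and must be fixed. The protocol synopsis and the SAP name different deciding sets for the same primary claim, no section that I could read reconciles them, and SAP 5.7 does not record the change. This follows from the text alone and depends on no assumption.

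The numerical consequence is moderate and conditional. The 90% power is right for 5% loss. If total loss to the PPAS is 10% to 20%, overall power is about 88% to 80% with independent strains, or 89% to 83% with correlation 0.5. The two sets then disagree on the overall verdict in roughly 4% to 13% of trials, mostly as FAS success with PPAS failure. These figures assume random exclusions, equal SDs in the two arms and the plan's GMT ratio of 1.5. Non-random exclusions were not modelled.

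**What to change.** In SAP 5.1.1.1.2, replace the PPAS clause with: *the conclusion will be made from FAS results; the PPAS analysis is supportive*. Reword the last sentence of SAP 5.3.2 to match, with the FAS as the primary set and the PPAS as the sensitivity set. This restores the protocol's rule and puts the decision on the set for which the power was calculated. It costs two sentences and no new analysis, since both sets are already to be analysed.

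If the sponsor prefers the PPAS as the deciding set, three things are needed: a protocol amendment, an entry in SAP 5.7 with the justification, and a restated power calculation with an explicit PPAS exclusion rate.

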##### 9.1.2.2 Immunogenicity Assessment Methods

###### 9.1.2.2.1 Hemagglutination Inhibition

To support the primary and secondary objectives of this study, HAI Ab titers will be determined on all blood samples obtained at D0 and D28.

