#### **12.1.1.1.2 Statistical Methods**

The statistical methodology will be based on the use of the lower bound of the 2 sided 95% confidence intervals (CIs) of the ratio of post-vaccination GMTs between the QIV-HD and QIV-SD groups. The CIs will be calculated by normal approximation of log-transformed titers for GMTs.

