5.1.1 Hypotheses and Statistical Methods for Primary Objective

5.1.1.1 Superiority of QIV-HD to QIV-SD

5.1.1.1.1 Hypotheses

A superiority approach will be used to compare post-vaccination GMTs between QIV-HD and QIV-SD groups for each strain and in each age group using a 1-sided test with Type I error rate of 0.025 following the individual hypotheses:

$$H_0^s : \frac{GMT_{QIV-HD}^s}{GMT_{QIV-SD}^s} \leq 1 \Leftrightarrow \log_{10}(GMT_{QIV-HD}^s) - \log_{10}(GMT_{QIV-SD}^s) \leq 0$$

$$H_A^s : \frac{GMT_{QIV-HD}^s}{GMT_{QIV-SD}^s} > 1 \Leftrightarrow \log_{10}(GMT_{QIV-HD}^s) - \log_{10}(GMT_{QIV-SD}^s) > 0$$

where

s: strain

If superiority is demonstrated for post-vaccination GMTs for the 4 strains within a same age group, then the immunogenicity of QIV-HD will be considered as superior to QIV-SD in the corresponding age group.

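### The baseline-titer ANCOVA already planned as a sensitivity analysis could be the deciding analysis, adding power without new data

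*SAP*

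**What the plan says.** The protocol (Synopsis and section 12.1.1.1.2) and SAP section 5.1.1.1.2 decide superiority on the lower bound of the two-sided 95% CI of the D28 GMT ratio, by strain and age group. No covariate enters: "The CIs will be calculated by normal approximation of log-transformed titers for GMTs".

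The plan draws two levels of conclusion. If all four strains succeed within an age group, "then the immunogenicity of QIV-HD will be considered as superior to QIV-SD in the corresponding age group" (SAP 5.1.1.1.1). The full objective asks for more: "The superiority objective will be achieved if it is demonstrated for the 4 strains in each age groups" (SAP 5.1.1.1.2), which is eight successes out of eight.

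Baseline titers come with the planned data: "HAI Ab titers will be determined on all blood samples obtained at D0 and D28" (Protocol 9.1.2.2.1). The SAP gives them a supporting role, on both PPAS and FAS: "A sensitivity analysis will be performed with adjustment on the pre-vaccination HAI titers". The sample size (Protocol 12.5, SAP 5.5) uses unadjusted standard deviations and takes no credit for adjustment.

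The documents disagree on the deciding set. The Protocol Synopsis states: "Conclusions will be made based on the FAS results". SAP 5.1.1.1.2 states: "but the conclusion will be made from PPAS results". The sample size is set for the FAS: "Attrition rate: 5% in FAS".

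**The concern.** A pre-vaccination titer often predicts the post-vaccination titer. The SAP shares this expectation, since it gives variability due to baseline as a reason for the ANCOVA. Leaving that variability in the deciding interval makes it wider than it needs to be.

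What is at stake is a missed success; no false claim is at issue. With eight tests that must all succeed and about 90% planned power, there is little reserve for the full objective. Adjustment would also remove chance baseline imbalance from the estimate that decides. In a linear model on the log10 scale without interaction, the adjusted difference targets the same GMT ratio, so the hypotheses in SAP 5.1.1.1.1 would not change.

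**Working it through.** **Inputs from SAP 5.5 and 5.1.1.1.1**
- GMT ratio 1.5 for every strain, so δ = log10(1.5) = 0.1761.
- SD of log10 titer 0.6 for two strains and 0.5 for two. The plan gives these for the QIV-SD group; I use them in both groups.
- 385 randomized per vaccine and age group (one cell), less 5% attrition: 385 × 0.95 = 366.
- One-sided alpha 0.025 per test, no multiplicity adjustment.

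**Assumption.** Neither document gives the correlation r between log10 D0 and log10 D28 titers. I use r = 0.1, 0.2, 0.3 and 0.5.

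**Formulas**
- Residual SD after adjustment = SD × √(1 − r²).
- Standard error = residual SD × √(2/n).
- Power from the noncentral t distribution with noncentrality δ/SE and df 2n − 2 (2n − 3 with the covariate).
- With independent tests, age-group power = (p₀.₆ × p₀.₅)² and full-objective power = (p₀.₆ × p₀.₅)⁴.

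**Reproducing the plan.** At SD 0.6, SE = 0.6 × √(2/366) = 0.0444 and δ/SE = 3.97, giving 97.7%. At SD 0.5, SE = 0.0370 and δ/SE = 4.76, giving 99.7%. Both match SAP 5.5. Then (0.9775 × 0.9974)² = 95.1% per age group, and its square is 90.4%, in line with the stated 90%.

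**With adjustment.** For example, at r = 0.3 and SD 0.6 the residual SD is 0.6 × √0.91 = 0.572, SE = 0.0423 and δ/SE = 4.16, giving 98.6%.

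| r (assumed) | Power per strain, SD 0.6 / 0.5 | Per age group | Full objective |
|---|---|---|---|
| 0 (unadjusted) | 97.7% / 99.7% | 95.1% | 90.4% |
| 0.1 | 97.9% / 99.8% | 95.3% | 90.8% |
| 0.2 | 98.2% / 99.8% | 96.0% | 92.1% |
| 0.3 | 98.6% / 99.9% | 97.0% | 94.0% |
| 0.5 | 99.6% / 99.98% | 99.1% | 98.2% |

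**Precision.** The CI half-width factor for an SD 0.6 strain is 10^(1.96 × SE): 1.222 unadjusted, and 1.217, 1.210 or 1.189 at r = 0.2, 0.3 or 0.5. The equivalent unadjusted size, 366/(1 − r²), is 381, 402 or 488 per cell.

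**Correlated strains.** Suppose the four test statistics in an age group correlate at 0.7 (assumption). Age-group power then goes from 96.1% to 96.8%, 97.5% or 99.2% at r = 0.2, 0.3 or 0.5, and full-objective power from 92.4% to 93.7%, 95.1% or 98.4%. The gain is smaller but remains.

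**Missing D0 titer.** The FAS (Protocol 12.2.1, SAP 5.2.1) requires only a post-vaccination sample, so an ANCOVA without a rule would drop subjects who lack a D0 titer. If 5% lacked one (assumption) and were dropped, adjustment would break even at about r = √0.05 = 0.22. If instead their D0 value is filled with a mean pooled over both vaccine groups, the residual variance is SD² × (1 − 0.95 × r²), and full-objective power is 92.0%, 93.9% or 97.9% at r = 0.2, 0.3 or 0.5. In null simulations of this rule (120,000 runs per setting), one-sided type I error was 0.0245 to 0.0253. At a true ratio of 1.5 the mean adjusted ratio was 1.499 to 1.501 (40,000 runs).

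**If the PPAS decides.** Its expected size is not given. At assumed total exclusions of 10% or 15% (347 or 327 per cell), full-objective power is 87.7% or 84.1% unadjusted, and 92.1% or 89.5% at r = 0.3.

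**The case against.** The strongest reply is that nothing is broken. The documents agree on the unadjusted interval, its power reproduces, and the adjusted result will be reported anyway on both analysis sets. All that remains is which of two valid prespecified analyses decides. That is correct, and it is why this is put as an improvement.

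The gain also rests on a correlation that the documents do not supply, and at r = 0.1 it is only 0.4 points for the full objective. This stands as a limit on size. With every subject kept, though, none of the correlations shown gives a loss.

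Within one age group the gain is modest: 0.9, 1.9 or 4.0 points at r = 0.2, 0.3 or 0.5, and less with correlated strains. A miss in one age group leaves the other's conclusion standing. This also stands.

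The change has a regulatory cost, and Protocol 5.1.5 plans inclusion for October to November 2019, so time before the D28 analysis is short. The unadjusted analysis also needs no rule for a missing D0 titer. These are real costs, but the fill rule is simple, ignores vaccine group and held type I error near nominal in simulation.

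Finally, the FAS/PPAS conflict exists whichever analysis decides, and ANCOVA does not resolve it. The PPAS figures above show how thin the reserve could be; they are not an argument that the unadjusted method is wrong.

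**Conclusion.** The point holds as a missed efficiency gain; the planned analysis is valid. The deciding interval is unadjusted, the baseline titers are already planned, and the ANCOVA is already prespecified but does not decide. Making it primary would raise full-objective power from 90.4% to 92.1%, 94.0% or 98.2%, and age-group power from 95.1% to 96.0%, 97.0% or 99.1%, at r = 0.2, 0.3 or 0.5.

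These figures rest on the plan's effect and SDs, 366 per cell, equal SDs in the two vaccine groups, a linear relation on the log10 scale and independent tests. The main uncertainty is r. The change is worth making but is not essential to a valid trial.

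**What to change.** Before the first database lock and unblinding, amend the protocol and SAP as follows.

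- **Primary analysis.** For each strain and age group, fit an ANCOVA of log10 D28 titer on vaccine group and log10 D0 titer, with computed values as in SAP 4.4.2.1. Superiority is shown if the lower bound of the two-sided 95% CI of the adjusted GMT ratio exceeds 1.
- **Sensitivity analysis.** The unadjusted GMT ratio takes this role.
- **Missing D0 titer.** Use the mean observed log10 D0 titer for that strain and age group, both vaccine groups pooled. State this as an explicit exception to the no-imputation rules in Protocol 12.3.2 and SAP 5.3.2, so that no subject in the deciding set is dropped.
- **Deciding set.** Reconcile the Synopsis (FAS) with SAP 5.1.1.1.2 (PPAS) and apply the model to one named set.
- **Failed D0 blood draw.** One note in Protocol 5.1.4 has the subject vaccinated. Another note in that section, the Synopsis and the Table of Study Procedures say the opposite. These must be reconciled, because they determine whether subjects without a D0 titer can enter the analysis.

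Site, the other randomization stratum (Protocol 6.5), may be left out of the model; little gain is expected from it.

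**Cost.** No new data, visits or subjects, and the baseline-titer ANCOVA is already to be programmed. The change needs a SAP revision and a protocol amendment. If the amendment counts as substantial under Protocol 5.4, it needs ethics committee approval and submission to regulators in each participating country (Protocol section 3 names Belgium, France and Germany), all before unblinding.
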